### 5.2 Platform Trials: An Efficient Strategy to Accelerate Drug Development and Scientific Discovery

Traditionally, clinical trials are designed to test a single investigational therapy; does a single investigational product work? These trials include a prespecified number of treatment arms (generally limited to two or three arms) and have a finite duration based on the time required to answer the trial question. Moreover, each trial requires an expensive, ad hoc trial infrastructure that is dismantled at the end of the trial. In contrast, platform trials are designed to investigate multiple investigational products in parallel and sequentially with the capability to adapt over time. Platform trials do not have a pre- specified end date: the platform remains open long-term and is

available to evaluate new investigational products as they become available. The trial infrastructure is built at the beginning and is shared across different treatments, leading to both operational and statistical efficiencies. Each investigational product is compared to a shared combined concurrent and non-concurrent placebo group, which The Master Protocol incorporates for trial efficiency.

Platform trials are an ideal infrastructure to advance the scientific understanding of the disease and novel endpoints with a coordinated strategy. With the testing of multiple investigational products using a common protocol and uniform data and sample acquisition processes, the platform is designed to answer multiple scientific questions and to serve as a source of data that can be used to enhance the design of other research projects. Further, accumulated learnings about endpoint behavior can be leveraged to adapt the Master Protocol so that future investigational products will be studied using more efficient biomarkers, outcome measures, and analyses.

# 5.3 Study Design

The P2P Trial is a perpetual multi-center, multi-regimen clinical trial evaluating the safety and early efficacy of investigational products for the treatment of participants with stage 2B NSD. Participants will be recruited based on presence of n-asyn pathology as determined by n-asyn SAA or other validated biomarkers (as such become available) and dopaminergic dysfunction as determined by DAT SPECT imaging and clinical features as defined by inclusion criteria (see Table 3).

As a perpetual platform trial, it can continue to assess relevant NSD interventions with the Master Protocol as its guiding trial framework. There is a single Master Protocol dictating the conduct of the trial. The Master Protocol describes the overall framework of the platform trial, including the target population, inclusion and exclusion criteria, regimen assignment and randomization schemes, Master Protocol endpoints, schedule of assessments, trial design, the mechanism for adding and removing interventions, and the statistical methodology and recommended statistical methods for evaluating interventions.

Interventions (i.e., investigational products) are tested in trial regimens, in which a regimen denotes both the active intervention and placebo corresponding to an intervention. Each trial regimen is described in its own Regimen-Specific Sub Protocol (RSSP) to the Master Protocol. The RSSP will describe the nature of the intervention and its mechanism of action (MoA) including the mode and frequency of administration, dosage, the specific target population (to be selected within the pre-defined subsets of the Master Protocol), additional enrollment criteria (if any), stopping rules, and other specific intervention-related information and assessments (safety or other assessmentsthat may be in addition to those outlined in the Master Protocol).

# 5.4 Allocation to Regimen

PPMI participants that provide consent to the Master Protocol will be screened for both Master Protocol and all active RSSP level inclusion and exclusion criteria that are accessible at the time of screening. The schedule of screening activities will depend on the date of the last PPMI annual visit. Group A Screening is defined if screened into the Master Protocol <6 months from the last PPMI annual visit; \_Group B is defined if screened into the Master Protocol  $\geq$  6 months from the last PPMI annual visit. Those participants who meet the Master Protocol eligibility and are eligible

for at least one RSSP will be equally randomized to one of the *J* actively enrolling regimens for which they are eligible. During the trial, enrollment to a therapeutic product will be discontinued once the target number of randomized participants in that regimen has been reached, but may be discontinued early due to safety concerns.

# 5.5 Allocation to Intervention

After randomization to a specific RSSP, participants will be consented to the assigned RSSP and screened for any additional regimen specific inclusion and exclusion criteria. Participants meeting all additional regimen specific criteria will be randomized to the RSSP-specific active treatment or placebo in a prespecified *J*:1 ratio (see Figure 1). Participants who do not meet one or more regimen specific eligibility criteria will be given the option to be randomized to an alternate regimen (assuming at least one additional regimen is actively enrolling). Eligible participants who elect not to participate in their assigned regimen will not be allowed to be randomized to an alternative regimen.

# 5.6 Number of Planned Participants and Treatment Arms

The sample size for each regimen is approximately 125 participants on active treatment and at least 125 corresponding shared concurrent and non-concurrent placebo participants. In this trial, multiple investigational therapeutic products for NSD Stage 2B will be tested simultaneously or sequentially. These investigational products will be provided by different partners, including pharmaceutical companies or academic groups.

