- 9. Study participant has a current history of alcohol or drug use disorder, as defined in the Diagnostic and Statistical Manual of Mental Disorders: DSM-5-TR, within the previous 5 years before screening.
- 10. Clinically significant abnormalities in laboratory test results at the screening visit, including hepatic and renal panels, complete blood count, chemistry panel and urinalysis as determined by site investigator.
- 11. Presence of human immunodeficiency virus (HIV) infection based on either history or testing.
- 12. Any of the following:
  - Presence of hepatitis B surface antigen or positive HBV DNA at Screening
  - Positive hepatitis C antibody test result at Screening or within 3 months prior to starting study drug. NOTE: Participants with positive hepatitis C antibody due to prior resolved disease can be enrolled if a confirmatory negative hepatitis C ribonucleic acid (RNA) test is obtained. Where hepatitis C RNA testing is unavailable, a positive hepatitis C antibody test will lead to exclusion.

**Investigational products:** Multiple investigational products (i.e., interventions, or active agents, from different regimen partners) will be tested in this Platform Trial. Each investigational product will have an associated RSSP with the complete description of the tested product. Each active agent will have a matching placebo.

**Duration of treatment per arm:** All participants will remain on the originally assigned regimen-specific arm for a minimum of 24 months and will remain on the originally assigned regimen-specific arm until the last participant randomized to that RSSP has completed 24 months of follow-up on intervention or until 24 months since randomization have passed (if terminated early). The RSSP will be closed once all participants have completed the follow-up period.

**Randomization:** With *K* representing the number of actively enrolling regimens at a given time, the platform trial incorporates two stages of randomization.

- 1. Equal randomization to all eligible regimens based on information easily accessible at the time of screening, where each regimen contains both active treatment and placebo groups.

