# 7. INCLUSION/EXCLUSION CRITERIA

### 7.1 Inclusion Criteria

Participants will be eligible for inclusion in this Master Protocol if they meet the following criteria:

- 1. Enrollment in PPMI observational study
- 2. Able to provide informed consent.
- 3. Diagnosis of NSD Stage 2B (see Table 3)
- 4. Female participants of childbearing potential and male participants must agree to use contraception as detailed in the RSSP.
- 5. Age 60 years or older at Screening visit.

6. Meet any additional inclusion criteria accessible at the time of screening (if applicable) for at least one active RSSP

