### 7.2 Exclusion Criteria

Participants fulfilling any of the following criteria are not eligible for inclusion in this Master Protocol, or able to participate in an RSSP:

- 1. Received any of the drugs associated with symptomatic parkinsonism within 6 months of Randomization Visit (see Appendix 2).
- 2. Received dopaminergic therapy (levodopa or dopamine agonist) for NSD motor syndrome or cholinesterase inhibitors for NSD cognitive syndrome within 90 days prior to or at the time of randomization.
- 3. Any other medical or psychiatric condition or lab abnormality, which in the opinion of the site investigator might preclude Master Protocol participation.
- 4. Individuals taking any of the drugs that might interfere with the DaTscan read out unless they are willing and medically able to hold the medication for at least 5 half-lives before DAT SPECT imaging (see Appendix 1).
- 5. Women may not be pregnant, lactating or planning pregnancy during the Master Protocol.
- 6. Participation in other investigational drug studies less than 30 days prior to screening (unless specified otherwise in the RSSP).
- 7. History or current diagnosis of electrocardiogram (ECG) or cardiac abnormalities indicating significant risk of safety for participants such as:
  - a. Myocardial infarction, unstable angina pectoris, transient ischemic attack, stent placement or coronary artery bypass graft, any of those within 6 months of screening.
  - b. Cardiac failure [New York Heart Association (NYHA) functional class II-IV], stroke or clinically significant uncontrolled arterial hypertension.
  - c. Clinically significant cardiac arrhythmias (e.g., ventricular tachycardia), complete bundle branch block, high-grade AV block (e.g., bifascicular block, Mobitz type II- and third-degree AV block).
  - d. Resting QTcF >450 ms (in males) or >460 ms (in females) and < 300 ms (regardless of sex) at screening or inability to determine the QTcF interval.
  - e. Long QT syndrome, family history of idiopathic sudden death or congenital long QT syndrome.
- 8. Score "yes" on item 4 or item 5 of the Suicidal Ideation section of the C-SSRS, if this ideation occurred in the past 6 months, or "yes" on any item of the Suicidal Behavior section if this behavior occurred in the past 2 years, except for the "Non-Suicidal-Self Injurious Behavior" (item also included in the Suicidal Behavior section).

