  - The research participant may be re-screened after 6 months (or longer if required by the RSSP-specific intervention).
- A research participant completes all activities in the assigned RSSP.
  - The research participant may be re-screened 6 months after RSSP completion (or longer if required by the RSSP-specific intervention).
- A research participant is withdrawn due to an adverse event, or is discontinued by the SI.
  - The research participant cannot be considered for rescreening until 24 months after their date of randomization into the original RSSP. They may be re-screened 6 months after their expected 24 month visit in the original RSSP (or longer if required by the RSSP-specific intervention).

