### 9.11 End of RSSP and Master Protocol

Participants will complete the RSSP after the last randomized participant has had the opportunity to complete 24 months on intervention or until 24 months since randomization have passed (if terminated early), and after all RSSP related activities have been completed. Participants who complete all activities for end of a specific RSSP may remain in the MP if they continue to meet all eligibility requirements described in Section 7 and wish to be screened for another RSSP as outlined in Section 8.4. Participants who complete their assigned RSSP and do not wish to be screened/ or do not qualify for another RSSP, will complete their enrollment in the Master Protocol and continue follow-up through the PPMI study. In those cases, end of RSSP visit will serve as the end of Master Protocol visit. The RSSP will be closed once all participants have completed the follow-up period.

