For a specific regimen, "power" is defined as the probability of demonstrating success on at least one of the primary endpoints. The primary analysis population for each regimen includes shared concurrent and non-concurrent control participants. As a result, regimens that enter the platform trial later can be expected to see an increased power relative to that of the first regimen as a result. Assuming 95% of randomized participants within an RSSP fall into the < 7 MDS-UPDRS Part III baseline strata, Table 6 demonstrates the benefits of the stated criteria by showing the probability of success for the first regimen under various assumed true values for the change on each endpoint. The first regimen in the platform is estimated to have 74%, 84%, and 91% power to detect treatment effects when both of the endpoints achieve 30%, 35%, and 40% slowing of progression, respectively. Similarly, we have greater than 86% power to declare success if there is truly a 40% or greater reduction in slope/progression of MDS-UPDRS Part III as long as there is at least a simultaneous 30% or greater reduction in mean striatum SBR. Finally, we have around 83% or higher probability of declaring success if there is truly a 40% or greater reduction in slope/progression on the DAT SPECT imaging endpoint and at least a 30% reduction on slope/progression on the MDS-UPDRS Part III endpoint. The table also demonstrates that the overall type I error probability (probability of meeting the criteria when there is no true reduction for either endpoint) is well controlled at 10.3%. For more details about the operating characteristics for each regimen and the assumptions used to calculate power, refer to the Design Report Appendix in the P2P Statistical Analysis Plan.

UPDRS Slowing	DAT Slowing	Power
0%	0%	10.3%
0%	30%	49%
0%	40%	67%
0%	50%	82%
30%	0%	56%
30%	30%	74%
30%	40%	83%
30%	50%	91%
40%	0%	77%
40%	30%	86%

Table 6: Overall RSSP Power (Win on Either Endpoint)

40%	40%	91%
40%	50%	94%
50%	0%	92%
50%	30%	95%
50%	40%	97%
50%	50%	98%

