## **15.5 Analysis Populations**

ITT: The primary analysis for each analysis regimen is based on the intent to treat principle and includes all participants randomized to the active treatment arm of the analysis regimen and all

participants in a shared concurrent and non-concurrent control group, regardless of the adherence to the RSSP or duration of follow-up. The analysis shared control group includes all participants randomized to any control arm within any regimen who met the initial eligibility requirements for the specific RSSP of interest at randomization. All data gathered before the regimen's primary analysis date will be included in the regimen's primary analysis unless otherwise agreed upon and noted in the RSSP.

Per-Protocol: To assess the sensitivity of the results, and to obtain knowledge regarding potential effects when the protocol was strictly adhered to, we will also replicate the primary objective using a per protocol population. The PP population includes the subset of all ITT participants who satisfy the following conditions:

- Have satisfactory compliance to assigned treatment, as specified in the RSSP.
- Have no major protocol deviations due to "protocol compliance" (defined as any alteration/modification that has the potential to negatively impact participant safety, integrity of the RSSP, ability to draw conclusions from RSSP data, or affect the participant's willingness to participate in the RSSP)

Only data collected as part of the RSSP will be included in the per-protocol analysis (i.e., no PPMI data will be utilized for participants that drop out of the RSSP but remain in PPMI).

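### Later regimens may enrol re-entrants selected for still being Stage 2B, but the primary models that pool non-concurrent placebo have no term for prior participation

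*Protocol*

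**What the plan says.** **Re-entry.** Section 8.4 states: "The research participant may be re-screened 6 months after RSSP completion", or later if the intervention requires it. The synopsis sets the minimum stay: "All participants will remain on the originally assigned regimen-specific arm for a minimum of 24 months". Section 9.11 says that completers "may remain in the MP if they continue to meet all eligibility requirements described in Section 7".

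**What must be met again.** Section 7.1 item 3 requires "Diagnosis of NSD Stage 2B (see Table 3"). Section 7.2 item 2 excludes anyone who "Received dopaminergic therapy (levodopa or dopamine agonist) for NSD motor syndrome" within 90 days before randomisation, and likewise cholinesterase inhibitors for the cognitive syndrome. Section 8.4 also opens a shorter route, 6 months after a regimen is stopped for safety, and a route after withdrawal for an adverse event.

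**Who is compared.** Section 5.6 plans about 125 active participants and "at least 125 corresponding shared concurrent and non-concurrent placebo participants". Section 15.5 defines the shared control group for the primary analysis: it "includes all participants randomized to any control arm within any regimen who met the initial eligibility requirements" of the regimen in question.

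**The models.** The synopsis and Section 15.1 describe Bayesian repeated-measures models adjusted for the baseline Part III stratum (<7 or ≥7, with 95% expected in the lower one). The models have individual baselines and slopes, and allow heterogeneity across regimens that is attributed to minor differences in criteria or mode of administration. Prior participation is not mentioned.

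**Power.** Section 15.3 says that "regimens that enter the platform trial later can be expected to see an increased power relative to that of the first regimen".

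**The concern.** Completers who return have passed a filter that those who moved to Stage 3 or are on dopaminergic treatment do not pass. If remaining Stage 2B goes with slower decline, re-entrants will on average decline more slowly than first entrants.

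Second-stage randomisation spreads them evenly between a later regimen's active arm and its concurrent placebo. It does nothing for the placebo participants of earlier periods, who are pooled into the same control group and include no re-entrants if they enrolled before re-entry began. An inactive drug would then be compared with a control group that holds a smaller share of re-entrants. A regimen succeeds by winning on either endpoint, so a shift in both raises the chance of a false success.

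This is separate from one person contributing to two arms. It remains if each entry is treated as its own episode.

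**Working it through.** **1. Timing.** Minimum stay plus wait: 24 + 6 = 30 months from first randomisation for a completer.

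**2. Reproducing the plan's figures.** Inputs are the Table 5 prodromal two-year changes, SBR 0.12 (SD 0.20) and Part III 2.9 (SD 3.9), with 125 v 125 participants, one-sided 5% per endpoint, and endpoints taken as independent. The standard error (SE) is SD × √(2/125): 0.0253 for SBR and 0.493 for Part III. Power for either endpoint is 1 − (1 − p₁)(1 − p₂).

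| Slowing on both | Computed | Section 15.3 |
|---|---|---|
| 30% | 73.4% | 74% |
| 35% | 83.2% | 84% |
| 40% | 90.4% | 91% |

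Type I error is 1 − 0.95² = 9.75%, against a simulated 10.3%. Of the 16 rows in Table 6, 13 agree within 2 points. The three with slowing on DAT only come out lower (44%, 62% and 78% against 49%, 67% and 82%). The approximation is good enough for sizing.

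**3. Bias under full pooling.** Let r be the share of re-entrants in the later regimen (equal in active and concurrent placebo), k their mean rate of change relative to first entrants, and w the non-concurrent share of controls. With no drug effect, the active arm changes by m[1 − r(1 − k)]. The pooled control changes by m[1 − (1 − w)r(1 − k)]. The difference is m·w·r·(1 − k).

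With 125 active, 125 concurrent and 125 non-concurrent controls, w = 0.5. SE = SD × √(1/125 + 1/250), which is 0.0219 for SBR and 0.427 for Part III. Error per endpoint is Φ(bias/SE − 1.645).

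Example, r = 20% and k = 0.5:
- The difference is 0.5 × 0.20 × 0.5 = 5.0% of the first-entry change. Relative to the pooled control change this is 0.05/0.95 = 5.3% apparent slowing.
- SBR: 0.006/0.0219 = 0.27, error 8.5%.
- Part III: 0.145/0.427 = 0.34, error 9.6%.
- Either endpoint: 1 − 0.915 × 0.904 = 17.3%.

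| r | k | Either-endpoint error |
|---|---|---|
| 0 | – | 9.75% |
| 5% | 0.9 | about 10% |
| 10% | 0.9 | 10.4% |
| 10% | 0.4 | 13.9% |
| 20% | 0.6 | 15.5% |
| 20% | 0.5 | 17.3% |
| 30% | 0.4 | 25.6% |
| 20% | 1.25 | 7.1% |

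More non-concurrent controls raise w. With 250 of them (w = 0.67), the 20% and 0.6 case gives 18.5%.

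**4. What k might be.** Neither r nor k is in the documents. Suppose re-entrants are the lowest fraction f of prior change, and prior and later slopes correlate c. Then k = 1 − c × φ(z_f)/f × SD/mean. For f = 0.65 and c = 0.4, φ(z_f)/f is about 0.57. For Part III, k = 1 − 0.4 × 0.57 × 3.9/2.9 = 0.69. For SBR, k = 0.62. Over f from 0.5 to 0.8 and c from 0.2 to 0.6, k runs from 0.36 to 0.91 for Part III and from 0.20 to 0.88 for SBR. These are assumptions. The formula also supposes selection on the endpoint itself, which is stronger than the protocol's filter.

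**5. Where the bias is zero.** In the first regimen nobody can yet have completed and returned, so r = 0. With concurrent controls only, w = 0.

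**The case against.** A reader might infer that re-entrants are selected on the trial's primary outcomes and that the bias must favour the drug. The documents do not support this.

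- Under Tables 3 and 7, moving from Stage 2B to Stage 3 turns on item 1.1 with MoCA, and on Part II. Part III enters only as a floor of 5, and dopaminergic dysfunction only as a threshold. Neither has a limit in the worsening direction, so someone declining fast on Part III or SBR can still be Stage 2B. Selection on the primary slopes is indirect.
- Re-entrants are at least 30 months further along. Table 5 shows that, among people meeting Stage 2B criteria, the PD cohort worsens about twice as fast as the prodromal cohort (6.9 v 2.9; 0.26 v 0.12). Faster progression in re-entrants is therefore possible, and it reverses the bias.
- First entrants also come from a standing cohort and must be Stage 2B at screening, which narrows the contrast.
- Section 7 requires current Stage 2B and 90 days without levodopa or agonist. It does not require never having been treated, and the medication appendix lists other PD drugs as allowed.
- Placebo arms of intermediate regimens can themselves contain re-entrants, and the regimen-heterogeneity term may absorb part of the difference. Full pooling against controls with no re-entrants is the worst case.
- Section 15.3 refers operating characteristics and power assumptions to the SAP's Design Report Appendix, which was not available here.

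All of this stands as a limit on size and certainty. It does not remove the mechanism. The protocol itself fixes the re-entry rule, the pooled control group and the named adjustments. Individual random slopes describe variation between people and do not correct a difference in group means.

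**Conclusion.** The point holds as a possible, uncorrected bias in regimens that enrol re-entrants. False slowing is the likely direction because remaining Stage 2B and off levodopa or agonist is indirectly related to slower Part III and SBR progression, but the documents establish neither direction nor size.

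Under full pooling, Table 5 prodromal values and independent endpoints, either-endpoint error is about 10% to 26% for 5–30% re-entrants at 0.9 to 0.4 times the first-entry rate, against 9.75% without them. It is 7.1% at 20% re-entrants progressing 1.25 times as fast. The upper figures are worst cases.

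It would also be too strong to call the Section 15.3 sentence on increased power wrong. With 20% or 30% re-entrants at half speed and the adjustment below, power at 30% slowing on both endpoints is about 77% or 74%, no lower than the 73.4% that the same method gives for the first regimen. The sentence needs a stated assumption.

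**What to change.** **Section 15.1.** For any regimen that enrols re-entrants, add prior P2P randomisation (yes/no) and its interaction with time to both primary models. First-entry non-concurrent controls then inform only the first-entry slope, and re-entrant actives are compared with re-entrant controls. This corrects the imbalance in either direction.

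**Sensitivity analyses.** Add one restricted to first entries and one using concurrent controls only. Neither should be the primary analysis: the first drops randomised participants from the intention-to-treat population, and the second gives up the precision of the shared controls.

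**Section 15.3.** State that the increased power of later regimens assumes re-entrants progress like first entrants.

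**Cost.** Prior randomisation is already in the trial database, so no participants or procedures are added. With 125 active, 125 concurrent and 125 non-concurrent controls and 30% slowing on both endpoints, power is 82.6% without re-entrants. With 20% re-entrants who progress like first entrants, the adjustment takes it to 82.0%, a loss of 0.6 points. The larger fall to about 77% arises if re-entrants progress at half speed, and nearly all of it comes from that slower progression, not from the adjustment. The change should be settled before completers begin to return, so that it cannot look chosen after the data.
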